7.3.1.1. Kaplan-Meier Analysis

The primary endpoint of sustained responder rate at Week 76 will be estimated based on the Kaplan-Meier (KM) survival functions of time to 1st relapse (MBL volume ≥ 80 mL) along with 95% CI for sustained responder rate for each treatment group.

The 95% CI for the KM estimation of the sustained responder rate at Week 76 (Day 169) is calculated using the exponential Greenwood formula via log-log transformation of the survival function.

The 95% CI for treatment difference in sustained responder rates will be calculated via linear transformation of the difference in relapse free survival function with pooled variance, as follows:

$$[(\widehat{S}_R(t) - \widehat{S}_P(t)) - 1.96 \sqrt{\widehat{V}[\widehat{S}_R(t) - \widehat{S}_P(t)]}, (\widehat{S}_R(t) - \widehat{S}_P(t)) + 1.96 \sqrt{\widehat{V}[\widehat{S}_R(t) - \widehat{S}_P(t)]}].$$

Treatment difference in sustained responder rates at Week 76 between relugolix and placebo will be estimated along with 95% CI using the method described below.

Variance of treatment difference will be calculated using the formula:

$$\widehat{V}[\widehat{S}_R(t) - \widehat{S}_P(t)] = \widehat{V}[\widehat{S}_R(t)] + \widehat{V}[\widehat{S}_P(t)];$$

Where each of the variance of the KM estimate will be calculated using the Greenwood's formula

$$\hat{V}[\hat{S}(t)] = \hat{S}(t)^2 \sum_{t_i \leq t} \frac{d_i}{n_i(n_i - d_i)}$$

where n_i denotes the number of patients at risk at time t_i and d_i denotes the number of events observed at time t_i .

P-value for testing treatment difference in sustained responder rates at Week 76 between relugolix+E2/NETA and placebo will be derived using an appropriate test statistic, as described in the following steps.

Step A: The stratified test statistics via log-log transformation of the difference in survival curve at a fixed time point will be used to derive the -value (Klein et al. 2007).

$$x^2 = \frac{\left\{ \sum_{s=1}^M [\log(-\log(\widehat{S}_{R_s}(t))) - \log(-\log(\widehat{S}_{P_s}(t)))] \right\}^2}{\sum_{s=1}^M \left\{ \frac{V(\widehat{S}_{R_s}(t))}{[\widehat{S}_{R_s}(t) \log(\widehat{S}_{R_s}(t))]^2} + \frac{V(\widehat{S}_{P_s}(t))}{[\widehat{S}_{P_s}(t) \log(\widehat{S}_{P_s}(t))]^2} \right\}}$$

Where s is the s^{th} stratum in the total of M strata and $t = \text{Week 76 (Day 169)}$ in this case. Each stratified test statistics at a fixed time under two samples follows a chi-square distribution with one-degree freedom.

Step B: If the stratified test statistics cannot be calculated due to event having not occurred in certain stratum, unstratified test will be used instead.

Step C: If unstratified test is still not estimable, the stratified version of the Mantel-Haenszel test using pooled KM estimators in each stratum will be constructed as the following. This test statistics follows a chi-square distribution with one-degree freedom.

$$\chi_{MH}^2 = \frac{\left\{ \sum_{s=1}^M \frac{n_{R_s} n_{P_s}}{n_{R_s} + n_{P_s}} (\widehat{S}_{R_s}(t) - \widehat{S}_{P_s}(t)) \right\}^2}{\sum_{s=1}^M n_{R_s} n_{P_s} V(\widehat{S}_{pooled_s}(t))}$$

It is noted that sustained responder rate at Week 104 (Day 365) as a key secondary endpoint will be defined as the KM estimates from the same KM curves and will be analyzed using the same method as described above.

7.3.1.2. Censoring Rules

The censoring rules in the Kaplan-Meier method are described as the following (see Table 8):

- For patients with relapse (MBL volume ≥ 80 mL) during the randomized treatment period, they will be considered as having an event at the time of first relapse. The time of first relapse is the date of the earliest menstrual bleeding days within the first FP collection visit window in which the MBL volume is ≥ 80 mL.
- For patients who did not have relapse during the randomized treatment period and had complete FP collection at each scheduled visit during the randomized treatment period,

they will be considered as not having an event and will be censored at the last available FP collection visit date during the randomized treatment period.

- For patients who did not have relapse during the randomized treatment period and had incomplete or missing FP collection during the randomized treatment period, they will be considered as censored using the following censoring rules:
 - If patients did not have FP collection after Week 64 (ie, have up to 3 FP collection visits through Week 64), they will be censored at the date of the last available FP collection visit if there are no consecutive visits with incomplete or missing FP collection; they will be censored at the date of the last available FP collection visit prior to the consecutive visits with incomplete or missing FP collections if there are two or more consecutive visits with incomplete or missing FP collections.
 - If patients had FP collection after Week 64
 - did not have incomplete or missing FP collections at consecutive visits, they will be censored at the last available FP collection date during the randomized treatment period.
 - had two or more consecutive visits with incomplete or missing FP collections, they will be censored at the last available FP collection visit date prior to the two consecutive visits during the randomized treatment period.

The time to event or censoring will be summarized by the Kaplan-Meier method. If the event time or censoring time is after the target (Day 365), Day 365 will be used as the event time or censoring time.

A sensitivity analysis will be performed considering different censoring rules (see Section [7.3.4.3](#)).

Table 8: Censoring Rules for Kaplan-Meier Analysis During Randomized Treatment Period

Type of Patients	Event	Event Time ^a	Censored	Censoring Time ^a
Patients who experienced a relapse (MBL \geq 80 mL)	Yes	Date of first relapse	No	N/A
Patients who did not experience a relapse and had complete FP collection	No	N/A	Yes	Date of last available FP collection visit
Patients who did not have relapse and had incomplete or missing FP collection a. Patients did not have FP collection after Week 64 b. Patients had FP collection after Week 64 i. No incomplete or missing FP collection at consecutive visits ii. Incomplete or missing FP collection at two consecutive visits iii. Incomplete or missing FP collection at three or more consecutive visits	No	N/A	Yes	a. Use the date of last available FP collection visit if no consecutive visits with incomplete or missing FP collection; Use the date of last available FP collection visit prior to the consecutive visits with incomplete or missing FP collection. b. See below i. Date of last FP collection visit ii. Date of last available FP collection visit prior to the two consecutive visits with incomplete or missing FP collection iii. Date of last available FP collection visit prior to the three or more consecutive visits with incomplete or missing FP collection

Abbreviations: N/A = not applicable.

^aThe reference point for event (or censoring) time is defined as from date of first dose of randomized study drug.

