2.2. Sample Size Considerations

Because this is an extension of study MVT-601-3003, the sample size of this study was based on approximately the number of patients who completed a pivotal study (n = 780 patients in total), and who participated in the LTE study (n = 600 patients in total assuming about 20% dropout rate at 6 months from the pivotal studies). Assuming the proportion of responders at Week 52 in MVT-601-3003 LTE study is 60%, it was estimated that approximately 360 patients were to be randomized into this study.

With 360 patients, the study would have at least 90% power to detect a difference of 20% or greater between relugolix+ E2/NETA group and placebo group for the primary endpoint. The following assumptions were used to determine the sample size for this study:

- 2-sided type I error rate: 0.05
- Randomization: 1:1
- Responder rate for placebo group: 40%
- Responder rate for relugolix + E2/NETA group: 60%
- Dropout rate: 20%

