7.3.3. Identifying Responder Status and Incomplete Feminine Product Collection at Each Visit

For each schedule visit, responder (MBL volume < 80 mL) status and incomplete FP collection will be identified for each patient by checking compliance with FP collection against the patient's paper diary, as measured by FPRR, and reasons for no FP collection (as displayed in Table 9).

Table 9: Identifying Incomplete Feminine Product Collection and Derivation of Responder Status at Each Visit During Randomized Treatment Period

FP Collection (Yes/No)	Reason for No FP Collection (CRF page)	Observed MBL Volume	FPRR	Incomplete FP collection	Responder Status
Yes	N/A	< 80 mL	>80-100%	Complete	Yes
	N/A	≥ 80 mL	N/A	N/A	No
	N/A	< 80 mL	≤ 80%	Incomplete, Not acceptable	Missing
No	Amenorrheic	Set as 0 mL	100%	Complete	Yes
	Patient only had spotting that did not require the use of sanitary products	Set as 4.99 mL	100%	Complete	Yes
	Patient failed to collect used products per protocol	Missing	0%	Incomplete	Missing
	Retreatment visit; No product collection required	N/A	N/A	N/A	N/A
	Successful retreatment; No product collection required	N/A	N/A	N/A	N/A
	Other	Missing	0%	Incomplete	Missing

Abbreviations: FP = feminine product; FPRR = feminine product return rate; MBL = menstrual blood loss; N/A = not available.

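### An isolated last collection that Table 9 rejects as incomplete still sets the censoring date, so that interval counts as relapse-free; the bias in each arm is upward and probably small

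*SAP*

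**What the plan says.** The primary endpoint is the Kaplan-Meier probability, at Day 169, of having had no menstrual blood loss (MBL) of 80 mL or more on randomized treatment (SAP 7.3.1). Time to relapse and the Week 104 rate use the same censoring rules (SAP 7.3.1.1, 7.4.1.1, 7.4.1.2).

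For women who had feminine product (FP) collections after Week 64, did not relapse and had some incomplete or missing collection, SAP 7.3.1.2 states that if they "did not have incomplete or missing FP collections at consecutive visits, they will be censored at the last available FP collection date". Table 8 row b.i gives "i. Date of last FP collection visit". Row a uses the last available collection visit for women with no collection after Week 64 and no consecutive gaps. With two or more consecutive gaps, censoring moves back to before the run.

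Table 9 in SAP 7.3.3 decides which collections are usable. A returned collection below 80 mL with a return rate (FPRR) of 80% or less is "Incomplete, Not acceptable", and responder status is missing. A reading of 80 mL or more is non-response whatever the FPRR. Reported amenorrhea, or spotting without product use, counts as complete.

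**The concern.** The two sections use the same collection in opposite ways. Table 9 says it does not establish whether the woman responded. The censoring rule uses its date as the end of known relapse-free follow-up. Suppose the last returned collection reads 70 mL with half the bleeding days absent, and she then stops drug. She stays in the risk set, event-free, to that visit.

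The SAP avoids this when there are two consecutive gaps, but not when a single gap comes last, where no later collection speaks to her status. At stake are the primary endpoint and two of the three key secondary endpoints in the fixed testing sequence.

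**Working it through.** **The plan's own figure.** SAP 2.2 assumes "2-sided type I error rate: 0.05", "Randomization: 1:1", "Responder rate for placebo group: 40" and "Responder rate for relugolix + E2/NETA group: 60" (percent), and "Dropout rate: 20" (percent). Per arm for 90% power:

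n = [1.960 × √(2 × 0.5 × 0.5) + 1.282 × √(0.6 × 0.4 + 0.4 × 0.6)]² / 0.2² ≈ 130.

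That is 260 in total, or 260/0.8 = 325 with dropout. With a continuity correction it is 140 per arm, 280 in total and 350 with dropout. At 360 × 0.8 / 2 = 144 per arm, power is 92.8%, so the stated 90% holds as a lower bound. The planning rates are reused below.

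**Inputs for the bias.**
- True Week 76 rates S: 40% and 60% (SAP 2.2).
- Visits every 4 weeks (Protocol 6.2), so six intervals to Week 76.
- Constant relapse probability per interval, h = 1 − S^(1/6): 0.1416 for placebo and 0.0816 for relugolix.
- Early stopping of 20% spread evenly: c = 1 − 0.8^(1/6) = 0.0365 per interval.
- *Assumption:* f, the share of early stoppers whose last collection is returned, isolated and incomplete. Not in the documents; range 5% to 100%.
- *Assumption:* m, the probability that a relapse in such an interval reads below 80 mL. Not in the documents; 0.5 and 1.
- q = c × f is the proportion of women at risk who leave this way in each interval.

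**Formulas.** Only h(1 − qm) of the relapses is seen per interval.
- Rule as written: S = [1 − h(1 − qm)]^6.
- Censoring at the prior visit: S = [1 − h(1 − qm) / (1 − q + qh(1 − m))]^6.

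Example for placebo, f = 20%, m = 1: q = 0.0073, so [1 − 0.1416 × 0.9927]^6 = 0.403.

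**Week 76 results with m = 1** (true values 40.0 and 60.0, difference 20.0):

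| f, both arms | Placebo, rule as written | Relugolix, rule as written | Difference |
|---|---|---|---|
| 5% | 40.1 | 60.1 | 20.0 |
| 20% | 40.3 | 60.2 | 19.9 |
| 50% | 40.7 | 60.6 | 19.9 |
| 100% | 41.5 | 61.2 | 19.7 |

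Censoring at the prior visit returns 40.0 and 60.0 throughout. A simulation with 180 per arm at f = 20% also gave 40.3 and 60.2 under the rule as written.

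**Setting q directly, m = 1.** For q = 1%, 2% and 5% per interval, placebo reads 40.4, 40.8 and 42.0, and relugolix 60.3, 60.6 and 61.6. The share of randomized women leaving this way by Week 76 is q × Σ[(1 − q)(1 − h)]^k for k = 0 to 5. At q = 5% this is about 19% of placebo and 22% of relugolix, against total planned dropout of 20%.

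**Unequal arms, m = 1.** If only placebo is affected, the difference is 19.7 (f = 20%) or 18.5 (f = 100%). If only relugolix is affected, it is 20.2 or 21.2.

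**Partial masking.** With m = 0.5 and f = 20%, the rule as written gives 40.1 and 60.1, and censoring at the prior visit gives 39.9 and 59.9. At q = 1%, placebo is 40.2 under one and 39.8 under the other.

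**Informative incompleteness.** All of this assumes that relapse is no likelier in these intervals than in others. If every such collection hid a relapse, the f = 20% rates would be 38.3 and 57.4, so the rule as written would be 2.0 and 2.8 points too high.

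**Week 104.** Early stoppers at f = 20% add about 0.1 point (thirteen intervals, m = 1, the same 40% and 60% taken as illustrative). Women who finish the study with an incomplete last collection are also affected. If 20% of Week 104 collections were incomplete, (1 − h)^12 × (1 − 0.8h) with h = 0.0681 and 0.0385 gives 40.6 and 60.5, or +0.6 and +0.5.

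**The case against.** *Available* is undefined in 7.3.1.2 and could mean usable, which would make this an ambiguity rather than an error. That reading is possible but weak: Table 8 row b.i omits the word, Table 9 records the rejected collection as returned, and footnote c of Table 6 uses the last non-missing collection, not the last complete one. Even on that view, two programmers could derive different censoring dates.

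The affected group is narrow, and this stands. Women with consecutive gaps, a reading of 80 mL or more, or reported amenorrhea or spotting are unaffected. A woman who returned nothing at her last visit is plausibly censored earlier already. FPRR counts days rather than volume, so a low value does not show a relapse, and SAP 7.3.2.3 allows up to 7 extra days to return products from an ongoing bleed.

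Sensitivity Analysis 3 deals severely with women who have no collection after Week 64: they become events at the first incomplete or missing visit. For Week 76, only last collections at about Weeks 68 to 76 remain untested. After Week 64 it changes only runs of three or more visits. The completer analysis does not change the censoring rule, and the per-protocol deviations listed in SAP 5.2 do not name incomplete collection.

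A reader might infer that the rule inflates the treatment effect. The documents do not support that. With equal incompleteness the difference shrinks slightly. A low FPRR needs diary bleeding days, so more incomplete collections in placebo is the likelier imbalance, and that understates benefit.

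**Conclusion.** The inconsistency is in the text: a collection rejected for responder status still extends relapse-free follow-up. It concerns one pattern only, an isolated last collection that was returned, read below 80 mL and had FPRR of 80% or less, and it adds at most one 4-week interval per woman.

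If any relapses are masked, each arm's rate is biased upward. The size rests on f (or q) and m, which the documents do not give. A plausible range is roughly 0.1 to 0.8 points per arm: the low end is f = 5%, the high end q = 2% in placebo with full masking. It reaches about 1.5 if every early stopper is affected and 2.0 at q = 5%. The 2.8-point figure needs every such collection to hide a relapse.

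Differences as far from 20 as 18.5 or 21.2 require full masking, every early stopper affected, and all of it in one arm; they are limits, not expectations. This merits correction as a matter of consistency. It does not by itself threaten the primary conclusion under the planning assumptions.

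**What to change.** In SAP 7.3.1.2 and Table 8 rows a and b.i, set the censoring date to the last FP collection that Table 9 classes as complete, including reported amenorrhea or spotting. Extend Sensitivity Analysis 3 to women with collections after Week 64 by analysing an isolated incomplete last collection in two ways: censored at that visit, and as an event.

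The cost is one phrase, the matching derivation and one added sensitivity analysis. Affected women are censored about 4 weeks earlier. The repair is exact only under full masking. Incomplete collections reading 80 mL or more still count as events, so with partial masking the estimate errs slightly low, and at 50% masking by about as much as the present rule errs high. Hence the paired sensitivity analysis. An isolated incomplete visit in mid-course is still carried as relapse-free; there, at least, a later collection follows.

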7.3.4. Sensitivity Analyses

To assess the robustness of the primary analysis, the following sensitivity analyses of the primary endpoint (sustained responder rate) will be conducted at Week 76.

7.3.4.1. Sensitivity Analysis 1

To assess the potential impact of the length and full exposure of the treatment, the primary endpoint (sustained responder rate) will be analyzed for the Week 76 completers population as a sensitivity analysis as appropriate. The Week 76 completers population is defined as patients in the mITT population who completed 24 weeks of treatment.

7.3.4.2. Sensitivity Analysis 2

The primary endpoint will be analyzed on the Per-Protocol population as a sensitivity analysis, using the methods specified for the primary analysis (see definition of Per-Protocol population in Section 4.2.2).

7.3.4.3. Sensitivity Analysis 3

The primary endpoint will be analyzed on the mITT population as a sensitivity analysis, using different censoring rules for some of the patients who did not have relapse during the randomized treatment period and had incomplete or missing FP collection during the randomized treatment period, which are listed below. Except the differences in the two situations listed below, the censoring rules in Table 8 will be used. The differences are:

- If patients did not have FP collection after Week 64 (ie, have ≤ 3 FP collection visits), they will be considered as having an event at the date of the first visit with incomplete or missing FP collection during the randomized treatment period.
- If patients had FP collection after Week 64 and had three or more consecutive visits with incomplete or missing FP collection, they will be considered as having an event at the date of the first visit of the three or more consecutive visits with incomplete or missing FP collection during the randomized treatment period.

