7.4.1.1. Time to Relapse (Menstrual Blood Loss Volume \geq 80 mL)

For the endpoint of time to MBL volume \geq 80 mL (event) during the randomized treatment period, time-to-event will be defined as weeks from first dose of the randomized withdrawal study drug to first occurrence of MBL volume of \geq 80 mL. The corresponding menstruation start date will be considered as the event date. Patients without an event will be censored by following the same censoring rules described in Section 7.3.1.2. Kaplan-Meier methods will be used to describe the time to event (relapse) distributions for each study treatment group from which median time to event will be derived. Hazard ratio (95%CI) of relugolix + E2/NETA to placebo for risk of relapse (MBL volume \geq 80mL) will be provided using a proportional hazard model stratified by the stratification factors (pivotal study baseline MBL volume (< 225 ml vs. \geq 225 mL) and duration of exposure to relugolix (28 weeks vs. 52 weeks). p-value for comparison of relugolix + E2/NETA to placebo based on the stratified log-rank test will be provided.

7.4.1.2. Proportion of Patients Who Maintained a Menstrual Blood Loss Volume of < 80 mL at Week 104

The proportion of patients who maintained a menstrual blood loss volume of < 80 mL by Week 104 (52 weeks of the randomized treatment period) as measured by the alkaline hematin method will be analyzed using the same method as that for primary efficacy endpoint described in Section 7.3. It is noted that sustained responder rate at Week 104 (Day 365) will be defined as the KM estimates from the same KM curves and will be analyzed using the same method as for the primary endpoint (see Section 7.3.1).

No subgroup analysis will be performed for this secondary efficacy endpoint.

The proportion of patients who maintained a menstrual blood loss volume of < 80 mL will also be summarized during the cumulative treatment period (including both randomized treatment period and the retreatment period).

The proportion of patients who had a menstrual blood loss volume of < 80 mL at a visit will also be summarized descriptively by visit during the cumulative treatment period (including both randomized treatment period and the retreatment period).

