7.4.2. Other Secondary Endpoints

7.4.2.1. Proportion of Patients Who Responded to Retreatment During the Retreatment Period

Proportion of patients who responded (MBL volume of < 80 mL) to retreatment with open-label relugolix 40 mg +E2/NETA during the retreatment period among placebo patients whose MBL volume had returned to \geq 80 mL during the randomized treatment period will be summarized descriptively. The point estimate and its corresponding 95% CIs will be provided.

The change and percent change in MBL volume from retreatment initiation will also be summarized descriptively as a continuous variable every 4 weeks after retreatment initiation during the retreatment period.

7.4.2.2. Change and Percent Change from Week 52/Baseline in Menstrual Blood Loss Volume During the Randomized Treatment Period

The change (for all patients) and percent change (for patients who did not have amenorrhea at baseline) in MBL volume from Week 52/baseline will be summarized descriptively as a continuous variable at each visit during the randomized treatment period including Week 76 and Week 104 visits. Observed MBL volume for each timepoint will be used to calculate change and percent change from Week 52/Baseline. In addition, the change and percent change in MBL volume from Week 52/baseline will also be summarized descriptively as a continuous variable at each visit during the cumulative treatment period.

For change and percent change in MBL volume, mixed-effects model will not be used to derive LS means (and 95% CIs) due to skewed distribution of MBL volumes (majority of patients experiencing amenorrhea with MBL volume set as 0 mL at baseline). Descriptive statistics (medians and simple means) will be provided for each treatment group.

Categorical summary of change in MBL volume will be provided by grouping patients into three categories: who had increase, no change, and decrease in MBL volume from Week 52/Baseline over time by visit for cumulative treatment period. A figure will also be provided to display the percentages for each category by treatment group every 12 weeks from Week 52/Baseline up to Week 104.

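### Only women who never relapse are censored before a two-visit collection gap, so censoring in the Kaplan-Meier analyses depends on the later outcome, and no planned sensitivity analysis tests this

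*SAP*

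**What the plan says.** SAP 7.3.1.2 and its Table 8 first sort women by whether they relapse at any time in the randomized period.

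- Relapsers: "For patients with relapse (MBL volume ≥ 80 mL) during the randomized treatment period, they will be considered as having an event", dated at the first relapse. Nothing is said about collections missed before it.
- The gap rule belongs to a separate Table 8 row: "Patients who did not have relapse and had incomplete or missing FP collection". Within it, those who "had two or more consecutive visits with incomplete or missing FP collections, they will be censored at the last available FP collection visit date" before the gap.

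The same rules reach two key secondary endpoints. For time to relapse (SAP 7.4.1.1), "Patients without an event will be censored by following the same censoring rules described in Section 7.3.1.2". The Week 104 sustained responder rate (SAP 7.3.1.1) "as a key secondary endpoint will be defined as the KM estimates from the same KM curves".

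Among the sensitivity analyses in SAP 7.3.4, the first two change the population (Week 76 completers; Per-Protocol) and add no gap rule. The third works by "using different censoring rules for some of the patients who did not have relapse during the randomized treatment period". It recodes as events non-relapsers with no collection after Week 64 and those with gaps of three or more visits, and otherwise keeps Table 8.

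**The concern.** Kaplan-Meier estimation requires that, given what is known at the time, being censored carries no information about later relapse. Here the decision to censor at a gap is made with knowledge of what happened up to Week 104.

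Take two women who both miss Weeks 60 and 64 and then resume collection. One relapses at Week 96: she stays at risk, counts as relapse-free at Day 169, and is an event at Week 96. The other never relapses: she is censored at Week 56 and all her later relapse-free collections leave the curve. Follow-up is removed selectively from women with the good outcome.

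The affected analyses are the first three tests in the fixed sequence of SAP 7.4.1. At stake are the reported rates and, if gaps differ between arms, the error rate of the later tests. Only gaps followed by resumed collection matter. If collection never resumes, no later relapse can be seen and the two groups cannot be treated differently.

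**Working it through.** **Plan's own figure.** SAP 2.2 gives 60% vs 40%, two-sided 0.05, 360 women and 20% dropout, hence 180 × 0.8 = 144 per arm. Power = Φ[(0.20·√144 − 1.96·√(2·0.5·0.5)) / √(0.6·0.4 + 0.4·0.6)] = Φ[(2.400 − 1.386)/0.693] = Φ(1.46) = 92.8%. The stated power of at least 90% reproduces.

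**Inputs.** Week 76 rates are from SAP 2.2. A constant hazard is assumed, so S(365) = S(169)^(365/169): 0.6^2.160 = 0.332 and 0.4^2.160 = 0.138. The true Week 104 difference is 19.4 points and the hazard ratio ln 0.6/ln 0.4 = 0.557. With 180 per arm and no dropout, the SE of the difference is 5.16 points at Week 76 and 4.35 at Week 104. The gap share g is not in the documents: 5-10% is taken as plausible and 20% as an upper end.

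**Hand check (limiting case).** Let a share g of an arm have its gap at the first two visits. Gap women who never relapse (g·S) leave at the start; all others stay. The SAP rule then estimates the Week 104 rate as S(1 − g)/(1 − gS).

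| g | relugolix (true 33.2%) | placebo (true 13.8%) |
|---|---|---|
| 5% | 0.315/0.983 = 32.1% | 0.131/0.993 = 13.2% |
| 10% | 0.299/0.967 = 30.9% | 0.124/0.986 = 12.6% |
| 20% | 0.265/0.934 = 28.4% | 0.111/0.972 = 11.4% |

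At g = 10%, 180 × 0.10 × 0.332 = 6.0 relugolix women and 180 × 0.10 × 0.138 = 2.5 placebo women lose follow-up.

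**Simulation, equal gaps in both arms.** There are 13 four-weekly visits and one resumed two-visit gap unrelated to bleeding, starting uniformly over the year, before Week 76 or after it. A relapse inside the gap is seen, found at the next collection, or missed. Each case uses 1,000,000 women per arm. Results under the SAP rule:

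| | 5% gaps | 10% | 20% |
|---|---|---|---|
| Week 76 bias per arm (points) | −0.5 to +0.3 | −1.0 to +0.6 | −2.1 to +1.2 |
| Week 76 difference (true 20.0) | 19.7-20.0 | 19.4-20.0 | 18.8-20.0 |
| Week 104 bias per arm (points) | −1.0 to −0.2 | −2.1 to −0.5 | −4.4 to −1.1 |
| Week 104 difference (true 19.4) | 18.9-19.2 | 18.4-19.1 | 17.3-18.7 |
| Hazard ratio (true 0.557) | 0.559-0.564 | 0.561-0.571 | 0.565-0.586 |

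Tests used 180 per arm and the unstratified form of the SAP's log-log test, plus the log-rank test. Type I error is 4.5-5.4%. Week 76 power is 93.5-96.5%, against 95.6-97.0% when gaps are ignored for everyone.

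**Unequal gaps, no true effect.** At 5% vs 20%, ungated type I error is 4.7-6.4% at Week 76, 5.4-8.9% for time to relapse and 6.4-10.6% at Week 104. Ignoring gaps for everyone keeps all three at 4.5-5.5%. At 5% vs 10% the SAP rule gives 4.6-5.5%. A separately written simulation gave 7.4-8.7% at Week 104 for 5% vs 20%, and about 5% when everyone is censored at the gap.

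**Symmetric rules compared.** Bias per arm in points, Week 76; Week 104:

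| Situation | Ignore gaps for all | Censor all at gap | SAP rule |
|---|---|---|---|
| Random gaps 5-20%, relapse seen or found next | 0.0 to +0.4; 0.0 | within 0.1 | as above |
| Random gaps 5-20%, relapse in gap missed | 0.0 to +2.8; +0.3 to +1.2 | within 0.1 | as above |
| 10% random gaps, and 5-10% of relapses trigger a gap and are found next | 0 to +1.5; 0 to +0.5 | +1.4 to +3.5; +1.2 to +3.7 | −1.0 to +1.3; −2.1 to −0.4 |

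If relapses trigger gaps and are also missed, ignoring gaps overstates by up to 5.5 and 4.3 points and the SAP rule by up to 4.2 and 1.4.

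**The case against.** The best case against is that little changes. At 5-10% equal gaps the difference moves by at most 0.6 points at Week 76 and 1.0 at Week 104, toward the null and small beside the standard errors. That stands.

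The raised error rates need a 5% vs 20% imbalance that nothing in the documents suggests, and they are ungated. In a simulation with no effect anywhere and that imbalance, Week 76 and Week 104 both rejected in only 1.1-2.6% of trials, before the intervening time-to-relapse gate. That also stands. A reader might infer that the primary result or the familywise error rate is compromised; the documents do not support that.

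A reader might also infer that the plan would reveal nothing about missing collections. That goes too far. SAP 4.1 calls for counts of non-missing values and numbers at risk, SAP 7.3.2.5 derives return rates by visit, and SAP 7.4.2.2 summarizes blood loss by visit and arm: "Observed MBL volume for each timepoint will be used to calculate change and percent change from Week 52/Baseline". These show missingness in part, and post-gap values still appear descriptively. What is absent is a count of resumed consecutive gaps.

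Finally, gaps may be related to bleeding. Under SAP 7.3.3, "responder (MBL volume < 80 mL) status and incomplete FP collection will be identified for each patient by checking compliance with FP collection", and reported amenorrhea or spotting counts as complete, so an incomplete return arises only in a woman who bled and used products. This limits the magnitude figures, which assume unrelated gaps. It does not rescue a rule that looks ahead.

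**Conclusion.** The defect is real as a matter of structure: the gap rule is conditional on never relapsing, it feeds three alpha-controlled analyses, and no planned sensitivity analysis removes the condition. Sensitivity Analysis 3 comes closest but alters only non-relapsers, and it leaves an exactly two-visit gap followed by collection after Week 64 as in the primary analysis.

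Its practical weight is modest: negligible for the Week 76 result and the tests under equal gaps, and a downward bias in the Week 104 rates of 0.2-1.0 points per arm at 5% gaps, rising to 1.1-4.4 at 20%. These sizes rest on assumed gap shares, a constant hazard and gaps unrelated to bleeding; gaps linked to bleeding could change both size and direction. The reading of the rule is firm and the size is not.

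It would also be tempting to conclude that one symmetric rule should replace Table 8. Which rule is less biased depends on why gaps occur, and the documents do not say.

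**What to change.** Apply one gap rule to relapsers and non-relapsers alike. At minimum, prespecify two sensitivity analyses for the Week 76 rate, time to relapse and the Week 104 rate:

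- (a) Ignore gaps for everyone: every observed relapse is an event, and women without relapse are censored at their last available complete collection.
- (b) Censor everyone at the last collection before the first gap of two or more visits, whatever happens later.

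Also tabulate the frequency and timing of resumed consecutive gaps by arm. Keep the Table 9 rule that a collection of 80 mL or more is a relapse whatever the return rate; it is sound.

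The cost is two analyses and one table from data already collected. Each analysis has a known weakness. (a) can overstate response if relapses start in or cause gaps, though Protocol 6.5.1.2 limits this by continuing collection until a heavy bleed is measured. (b) is biased upward if relapse makes a gap more likely. Neither is put forward here as the primary rule; agreement between them, read with the gap table, would settle the question.
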